Aim 1: To develop a complex intervention to increase uptake of testing for HIV among household members by reducing perceptions of stigma associated with HIV and testing for HIV. Lay health workers (LHWs) will deliver a novel invitation strategy for HIV testing in 20 purposively sampled households that includes 1) acceptance-optimized sequencing, 2) prosocial messaging, and 3) salivary HIV testing. We will administer HIV and TB stigma scales before and after the invitation. We will interview all household members following the visit and engage LHWs in focus group discussions to explore feasibility and acceptability of the invitation strategy. We will iteratively refine the intervention to optimize acceptability and reductions in perceived stigma, for evaluation in Aim 2.

Aim 2: To evaluate the intervention on household HIV stigma and uptake of testing among household members undergoing TB contact investigation in a household-randomized pilot trial. We will recruit a prospective cohort of multiple-contact households undergoing routine contact investigation for TB. Households will be randomized to one of two study arms. Households in the control arm will receive routine household contact investigation services, including free, optional oral HIV testing. Households in the intervention arm will receive routine household contact investigation services and free, optional oral HIV testing with the social-behavioral framing intervention. LHWs in the intervention arm will use acceptance-optimized sequencing of invitations and a prosocial invitation script to offer salivary testing for HIV to household members. We will measure our co-primary outcomes of HIV and TB stigma using standardized instruments before invitation and after completion of post-test counseling. We will measure the proportion consenting to HIV testing, yield of HIV diagnoses, and the proportion of new PLWH linked to HIV care at 1 month and reassess household HIV and TB stigma at 3 months in a subset of participating households. Participants may also be contacted at a later point for interviews, focus-group discussions or surveys to better understand the implementation and impact of the intervention.

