The expected impact of these studies is to generate preliminary data on a novel approach to offering home testing that reduces perceived stigma within households and its effects on testing and linkage to and retention in care, built on the scientific premise of longstanding research on group processes and social decision-making. These data will inform a future randomized study evaluating the clinical impact of these new stigma-reducing approaches to offering and delivering HIV counseling and testing. Our proposal aligns with NIH priorities for interventions that increase access to HIV care and reduce the effects of stigma on PLWH, PLWH with TB, and adolescents and children.

2. **Probable Duration of Project:** State the expected duration of the project, including all follow-up and data analysis activities.

The activities described here will take place from April 1, 2019 until approximately March 30, 2021.

3. **Background:** Describe the background information that led to the plan for this project. Provide references to support the expectation of obtaining useful scientific data.

UNAIDS has called for 90% of persons living with HIV (PLWH) to know their HIV status by 2020^{1,2}; the World Health Organization (WHO) has called for elimination of active TB as a public health threat by 2035. Nonetheless, major gaps exist: one-third of PLWH do not know their status; similarly, almost 40% of TB patients go undiagnosed each year. To reach these ambitious targets, HIV testing services must reach another 7.5 million people by 2020, and TB testing services another 4 million people.³ New data from the Population-based HIV Impact Project show that achieving high status awareness is a greater challenge than achieving high antiretroviral therapy uptake or viral load suppression in 7 Southern African countries, including Uganda.⁴

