LHWs will carry out home visits in pairs or with 3 LHWs dependent on the needs of that household. A LHW employed by the clinics will provide routine contact investigation services and a trained study LHW will collect research data and deliver the intervention for those randomized to the intervention arm of the study. While the LHW carries out standard contact investigation screening, the study LHW will administer a short HIV-TB stigma scale individually to all consenting adult members of the household in both arms. The research LHW will follow the assigned script based on randomization allocation to identify household members who are eligible and invite them to test for HIV, recording time-stamped offers, test decisions, and test results. The research LHW will collect household- and individual-level demographic, socioeconomic data, stigma scales, measures of household stability, including household tenure in years as well as relationship to and perceived influence of household members and clinical data using a structured survey.

Procedures for all households: Upon arrival, the CHWs will enroll all eligible, consenting household contacts in the study. But before doing this, at the start, CHWs will introduce themselves and ask for introduction of contacts. At this time the master list of all the contacts will be created.

- They will introduce the reason for their visit and the services they will offer (TBCI, oral HIV testing) using the introductory script for either Intervention or Routine Contact Investigation households, depending on the household assignment.
- For the intervention arm, one CHW will take the index case to a private area to ask the influence questions using the paper form (master list) as a key. After completing this exercise, the CHW will then embark conducting household contact screening interviews followed by HIV testing and any other study related activities. All data will be collected via CommCare.
- Meanwhile, the other CHW will be conducting routine TB contact investigation activities and any other clinical procedures in household TB contact investigation. Details of these procedures are found below:

a) Index case influence questions

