After enrollment, CHWs will introduce themselves and ask for the introduction of contacts and it is at this time when a contacts master list will be created. Index patients will then be asked the influence questions. The questions will be asked in two steps, once to capture the number and once to capture the name. The other CHW will go head to conduct routine TB contact investigation activities.

b) Household contact screening interview

After household contact enrolment, each contact will undergo a short interview. This interview will capture age, gender, occupation (if applicable), income (if applicable), education in years, relationship to index patient, history of testing for HIV, month and year of last HIV test, and self-reported symptoms of TB (including cough, subjective fever, or weight loss).

The short (13-item) version of the Van Rie TB- and HIV-related stigma scales will be administered immediately prior to TB screening, as well as at the conclusion of the visit. We will ask the index patient to share the number of rooms in the dwelling, the number of windows in the dwelling, and the number of individuals (including children) who dwell there. All screening interview components will be conducted by a CHW. Screening interview components are identical for all study groups.

c) HIV testing procedures

Working in teams of two, CHWs will provide household contact investigation services, including offering oral HIV testing. One CHW will lead and accompany each HIV test while a colleague leads other household members through TB screening.

To begin, the CHW responsible for offering HIV testing will individually invite the client to a place apart from the others. S/he will detail the process of HIV testing in Luganda and/or English, per client preference. A pictorial guide may be used to help walk the client through each step of the process using a Luganda- or English-language guide. The CHW will then provide pre-test counselling.

Consenting household contacts who choose to test for HIV will swab their own gums. CHWs will be fully trained to provide HIV counselling and support throughout all testing procedures.

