Randomization: For aim 2 of the study, variable block randomization will be done at the level of the household and will be performed at the time of household enrollment. Block sizes will have a minimum of 2, a maximum of 6. We will utilize study randomizer, an online randomization tool with concealed randomization. When a CHW has deemed an index patient and their household to be eligible for the study, and after the index patient or their guardian has provided verbal informed consent, the CHW will place a phone call to the study coordinator. The study coordinator will then enroll the household using the study randomizer tool and let the CHW know the study allocation. The CHW will then fill in the appropriate allocation, along with the randomization ID, and contact the appropriate CHW team for the household visit.

Households randomized to intervention group will be offered oral testing with the social-behavioral intervention. Households randomized to the standard of care group will be offered oral testing without any social-behavioral intervention. CHWs will operate in teams that are always assigned to the same arm of the study. There will be three teams of CHWs in total: one intervention group, one standard of care group, and one clinic-based group that will always be in charge of initial enrollment of index patients and recording any clinic follow up by individuals in either arm of the study.

Integrated intervention. In Intervention Households only, the CHW will present the opportunity to test using the script and procedures described in the next section (“Specification of intervention components”). This script communicates that the individual is completely free to opt out of testing, but that testing is the norm. We will use “Opt-Out” testing language along with language letting them know that they can decline.

If the household contact decides to opt out of HIV testing, the CHW will carry out a survey. These questions will take approximately the same amount of time as HIV testing and counselling procedures (~20 to 30 minutes) in order to blind other household members from the testing decision of that household contact. Contact decisions to test or not to test as well as test results will be recorded in CommCare.

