In the Aim 2 analysis, we will calculate and compare uptake across each of the trial arms using an intention-to-treat analysis. We will also consider a per protocol analysis and model adjusted for imbalances in baseline confounders as secondary analyses. To test the hypothesis that a norming intervention can increase test uptake, we will compare testing uptake among the intervention households and control households using cluster-adjusted chi-squared tests of proportion and by fitting mixed effects logistic regression models with two levels (household, contact.) To test the hypothesis that invitation scripts that apply acceptance-optimized sequencing of oral test offers and prosocial messaging can decrease HIV stigma within households, we will evaluate change in HIV-TB stigma using cluster-adjusted dependent t-tests and fitting multilevel models with clustered standard errors. We will conduct a causal mediation analysis to determine to what degree the effects of the intervention on stigma explain the improvement in test uptake using observed-variable structural equation modeling. All hypothesis tests will be carried out at alpha of 0.05, corrected for multiple tests as appropriate. We will report household ICC for stigma as well as test uptake and will consider a household ICC of >0.2 a sufficient level of clustering necessitating adjustment.

SECTION II: RESEARCH INVOLVING DRUGS, BIOLOGICS, RADIOTRACERS, PLACEBOS AND DEVICES

If this section (or one of its parts, A or B) is not applicable, check off N/A and delete the rest of the section.

A. RADIOTRACERS N/A

B. DRUGS/BIOLOGICS N/A

B. DEVICES N/A

SECTION III: RECRUITMENT/CONSENT AND ASSENT PROCEDURES**1. Targeted Enrollment: Give the number of subjects:**

- a. Targeted for enrollment at Yale for this protocol: 0
- b. If this is a multi-site study, give the total number of subjects targeted across all sites:
 - 40 to 60 individuals drawn from 20 households (Aim 1)
 - Approximately 8 to 15 lay health workers with experience carrying out TB contact investigation
 - Approximately 60-100 health workers participating in HIV and TB care services during the COVID-19 pandemic
 - Approximately 152 index patients and their approximately 304 household contacts (Aim 2)

2. Indicate recruitment methods below. Attach copies of any recruitment materials that will be used.

 Flyers	 Internet/web postings	 Radio

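### The causal mediation analysis names no stigma score, and none is scheduled between a contact's own test offer and the decision, so how far stigma explains uptake is not identified

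*Combined protocol and SAP*

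**What the plan says.** Section I, item 13 (Statistical Considerations) commits to a quantitative causal statement: "We will conduct a causal mediation analysis to determine to what degree the effects of the intervention on stigma explain the improvement in test uptake". The method is an observed-variable structural equation model. The item does not say whether the mediator is HIV or TB stigma, a single score or a change, or an individual or a household score. It lists no confounders of stigma and testing, no identifying assumptions and no sensitivity analysis, and it does not call the analysis exploratory.

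The timing of the stigma scales is given in three places, which agree:

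- Item 1, Aim 2: "before invitation and after completion of post-test counseling".
- Item 4, household contact screening interview: the 13-item scales "will be administered immediately prior to TB screening, as well as at the conclusion of the visit".
- Item 4, TB and HIV stigma scales: at the start of the home visit and at its end.

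Item 4, Follow-up interview, adds a 3-month score in a subset of households. The study worker's tasks during the visit include "recording time-stamped offers, test decisions, and test results". The plan's own stigma effect, in item 4 (Analysis) and item 13, is a change over the visit.

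**The concern.** A mediator has to follow the intervention and precede the outcome. Here the outcome is the decision to test, and it falls between the two visit scores. A score taken after the decision may be a consequence of testing. Before the final scale, testers receive education, a result and counselling (item 4, Administering the oral test and HIV test results). For those who decline, the Integrated intervention paragraph says: "If the household contact decides to opt out of HIV testing, the CHW will carry out a survey". If that difference in experience moves the final score, the model finds a stigma-uptake association that runs from testing to stigma and reports it as mediation.

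The mechanism statement is what is at stake. Item 1 says of this trial: "These data will inform a future randomized study evaluating the clinical impact of these new stigma-reducing approaches". A reported share of the uptake gain explained by stigma would be read as evidence that stigma reduction is the active ingredient.

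**Working it through.** **Step 1: time order of each candidate score**

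| Score | Relative to the contact's own offer | Relative to the decision | Consequence |
|---|---|---|---|
| First score, start of visit | before | before | cannot carry the effect of that contact's own prosocial, opt-out offer |
| End-of-visit score | after | after | can be changed by testing and counselling |
| Change over the visit | contains the end-of-visit score | contains a post-decision score | same problem |
| 3-month score (subset) | after | after | same problem, later still |

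Two qualifications apply to the first row. On arrival the visit is introduced "using the introductory script for either Intervention or Routine Contact Investigation households, depending on the household assignment", so the first score may already reflect an arm-specific introduction. Also, "One CHW will lead and accompany each HIV test while a colleague leads other household members through TB screening". A contact screened later may therefore already know that another member shared a decision to test. In neither case does the score follow the contact's own offer.

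**Step 2: the plan's own figures**

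The plan gives no figure for the mediation analysis. The uptake inputs used below are those of the sample-size section, and they reproduce its total. For 0.85 versus 0.98, two-sided alpha 0.05, 90% power and pooled variance, 95 contacts per arm are needed. With two contacts per household and ICC 0.59, the design effect is 1 + 0.59 = 1.59. Then 95 × 1.59 / 2 = 75.5, which rounds up to 76 households per arm, 152 in total, as stated.

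**Step 3: what the model reports when true mediation is zero**

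Assumed model: later stigma = −aT × arm − d × test + noise of variance 1, with no effect of stigma on testing. Here d is the amount by which testing lowers stigma and aT is any other arm effect on stigma, both in noise-SD units. The documents give neither.

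- Uptake difference: D = 0.98 − 0.85 = 0.13.
- Average within-arm variance of testing: v = (0.85 × 0.15 + 0.98 × 0.02) / 2 = 0.07355.
- Arm to stigma: a = −(aT + D × d).
- Stigma to testing, given arm: b = −d × v / (1 + d² × v).
- Spurious share = a × b / D. With aT = 0 this is d² × v / (1 + d² × v).

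Example, aT = 0 and d = 1.0: 0.07355 / 1.07355 = 6.85%. Example, aT = 0.4 and d = 1.0: 0.53 × 0.0685 / 0.13 = 27.9%.

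Spurious share of the 13-point gain, in %:

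| aT | d = −1.0 | −0.5 | −0.2 | 0 | 0.2 | 0.5 | 1.0 |
|---|---|---|---|---|---|---|---|
| 0 | 6.85 | 1.81 | 0.29 | 0 | 0.29 | 1.81 | 6.85 |
| 0.2 | −3.69 | −3.75 | −1.96 | 0 | 2.55 | 7.36 | 17.39 |
| 0.4 | −14.23 | −9.31 | −4.22 | 0 | 4.81 | 12.92 | 27.93 |

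The sample-size section also considers control uptake of 0.80 and 0.75. Keeping 0.98 in the intervention arm (an assumption), v is 0.0898 and 0.10355, and D is 0.18 and 0.23. For d from 0.2 to 1.0 the two cases together give 0.4% to 9.4% with aT = 0, and 2.2% to 26.6% with aT of 0.2 to 0.4.

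Clustering does not change this. A simulation of 1,000,000 two-contact households with uptake ICC 0.59, and stigma-noise ICC of 0 or 0.59, stayed within 0.1 percentage points of the formula for d from −0.2 to 1.0.

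**Step 4: a change score as mediator**

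With an assumed pre/post correlation of 0.7, the noise variance of the change is 2 × (1 − 0.7) = 0.6. At aT = 0 and d = 1.0 the share is 0.07355 / (0.6 + 0.07355) = 10.9%. At aT = 0.4 it is 0.53 × 0.1092 / 0.13 = 44.5%. A separate simulation at the planned size (152 households of two, 1,000 runs, aT = 0) gave about 3% at d = 0.5 and 12% at d = 1.0.

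**The case against.** The strongest reply is that the first score is not always free of the intervention. It may follow the arm-specific introduction and, for some contacts, another member's shared decision. Item 4 lists learning of that decision as a way to lower perceived stigma. For those contacts the first score has the right time order for that component. This stands, but it does not rescue the planned analysis. How many contacts it covers is unknown, since the scales section puts the first scale at the start of the visit. The plan uses that score as its before measurement, it omits the contact's own offer, and confounding of stigma with willingness to test is not dealt with. Randomisation identifies the arm effects on stigma and on uptake, but not the path from stigma to uptake. Time stamps order the events without adding a score.

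Second, the mediation sentence closely follows one about change in HIV-TB stigma, so the change score is the natural reading. That is fair, and it narrows what is left unnamed to HIV or TB and individual or household. It also selects a score that contains the post-decision measurement.

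Third, the illustration depends on the mediator and on assumed effects. This is correct. Step 4 shows larger shares for a change score, so the tabulated values are not bounds. The conclusion rests on time order, not on them.

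Fourth, this is one secondary, explanatory analysis in a pilot, and no go/no-go decision hangs on the mediated share. That limits the consequence. It does not make the causal reading valid.

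Fifth, the arm comparisons themselves are not cleanly stated: dependent t-tests for stigma, and for uptake a comparison with pre-implementation households in item 4 but with control households in item 13. That is a separate matter, which the change proposed here neither settles nor worsens.

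**Conclusion.** The concern holds. No scheduled stigma score follows a contact's own offer and precedes the decision, so the causal share promised in item 13 cannot be estimated from these data, and more households would not help. This is an error in what is claimed, not merely missing detail, because the analysis as written would count any effect of testing on stigma as mediation.

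The size and sign of the bias are unknown. It is zero if testing does not move stigma. At the planned uptake rates, with no true mediation and a later score as mediator, the illustration gives:

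- 0.3% to 6.9% if testing lowers stigma by 0.2 to 1.0 SD and the arm has no other effect on stigma;
- 2.5% to 27.9% over the same range with an added arm effect of 0.2 to 0.4 SD;
- −2.0% to −14.2% with that arm effect if testing raises stigma by 0.2 to 1.0 SD.

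These figures rest on a linear scale and on stigma effects assumed here. They show possible direction, not a likely size. The point should be corrected, and it makes no claim against the randomised comparisons of stigma change and of uptake.

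**What to change.** In item 13, remove the statement that stigma effects explain the improvement in uptake, and report the arm effect on stigma and the arm effect on uptake separately.

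If a mediation-type model is kept:

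- name the score: HIV or TB, individual or household, single or change;
- state its timing: end-of-visit, change and 3-month scores follow or contain a measurement after the decision, and the first score precedes the individual offer;
- label the result exploratory and associational;
- state the assumptions: time order, no unmeasured confounding of stigma and testing, and the outcome scale.

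The cost is a wording change to one sentence, with no new data, visits or households. What is lost is a causal mechanism statement that the measurement schedule cannot support.

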1. The test statistic is the effect regression coefficient from a mixed-effects logistic regression model
2. Alpha = 0.05
3. Power = 90%
4. The proportion consenting to testing in the control group will be 0.85
5. The proportion consenting to testing in the intervention group will be 0.98 (a difference of +0.13 vs the control group).
6. An average of two household contacts will be eligible for HIV testing per household. The intra-class correlation (ICC) will be 0.59.

The total number of households needed is sensitive to the mean cluster size. Under the preceding assumptions, the necessary number of households may range from 152 if the mean number of eligible contacts per households is 2 to 138 if the mean number of contacts per household is 3. The total

number of households needed is also sensitive to the ICC. Sample size estimates assuming a range of possible ICC values, ranging from the value observed during the preliminary research (0.59) to higher values (0.65, 0.70), are not presented here although considered by the study team. Finally, the total number of households needed is sensitive to the baseline (control group) proportion of tests accepted. Sample size estimates assuming three possible baseline testing rates (75%, 80%, and 85%) in control group households have been considered. We will plan an interim blinded power analysis by an external biostatistician to readjust sample size targets as necessary for actual mean cluster size and ICC after enrolling the first 100 households.

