Analysis. In the Aim 2 analysis, our primary outcome is change in perceived HIV-TB stigma after following the first household contact tracing visit; the secondary outcome is uptake of HIV testing; we will descriptively assess linkage to care from both baseline data and intervention households. We will calculate descriptive statistics for participant characteristics, and test associations between characteristics and perceived/attributed household stigma. To test the hypothesis that invitation scripts that apply acceptance-optimized sequencing of oral test offers and prosocial messaging can decrease HIV stigma within households, we will evaluate change in HIV-TB stigma using cluster-adjusted dependent t-tests and fitting multilevel models with clustered standard errors. To test the hypothesis that prosocial messaging and theory-informed sequencing of HIV test offers can increase test uptake, we will compare testing uptake among the intervention households and pre-implementation households using cluster-adjusted chi-squared tests of proportion and by fitting multilevel logistic regression models. All hypothesis tests will be carried out at alpha of 0.05, corrected for multiple tests as appropriate. We will report household ICC for stigma as well as test uptake.

5. Genetic Testing N/A

6. **Subject Population:** Provide a detailed description of the types of human subjects who will be recruited into this study.

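### The ICC >0.2 trigger for cluster adjustment conflicts with household randomisation and could permit an unadjusted test of the primary stigma outcome

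*Combined protocol and SAP*

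**What the plan says.** - **Unit of allocation.** Section I, item 4, Randomization: for Aim 2, "variable block randomization will be done at the level of the household".
- **Primary outcome.** Section I, item 4, Analysis (Aim 2): "our primary outcome is change in perceived HIV-TB stigma after following the first household contact tracing visit". Uptake of HIV testing is secondary there.
- **Planned tests.** For stigma, both that paragraph and item 13 state that "we will evaluate change in HIV-TB stigma using cluster-adjusted dependent t-tests and fitting multilevel models with clustered standard errors". For uptake, item 13 compares the arms "using cluster-adjusted chi-squared tests of proportion and by fitting mixed effects logistic regression models with two levels (household, contact"). No condition is attached to either.
- **The trigger.** Item 13 closes by promising household ICCs for both stigma and uptake, and adds that the team "will consider a household ICC of >0.2 a sufficient level of clustering necessitating adjustment". The Analysis paragraph in item 4 also promises the ICCs but sets no threshold.
- **Planning values.** Item 4, Sample Size (Aim 2): "An average of two household contacts will be eligible for HIV testing per household" and "The intra-class correlation (ICC) will be 0.59". The households needed are given as "152 if the mean number of eligible contacts per households is 2 to 138 if the mean number of contacts per household is 3". The 0.59 belongs to the uptake calculation. No ICC is given for stigma or for change in stigma.

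**The concern.** When households are allocated, the standard error of an arm comparison has to reflect household-level variation. The design creates that need, and a low ICC estimate from the trial data does not remove it. The estimate is itself noisy: with a true ICC of exactly 0.20, about half of such trials would estimate it at or below 0.2.

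The closing clause of item 13 makes adjustment look conditional, while the methods named in the same item and in item 4 are unconditional. Nothing says which governs. If the clause governs and stigma is only modestly correlated within households, the primary test is run with a standard error that is too small, and its true error exceeds the stated 0.05. If it is unclear which governs, an analyst can pick either test once the data are in and cite the protocol for both.

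**Working it through.** **1. The plan's own sample size already allows for clustering.** Inputs from item 4, Sample Size: control 0.85, intervention 0.98, alpha 0.05 (taken as two-sided), power 90%, ICC 0.59, 2 or 3 contacts per household.

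Contacts per arm before clustering, with mean proportion 0.915:

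(1.960·√(2·0.915·0.085) + 1.2816·√(0.85·0.15 + 0.98·0.02))² / 0.13² = (0.7730 + 0.4915)² / 0.0169 = 94.6

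Multiply by the design effect 1 + (m − 1)·ICC, divide by m, and round up per arm:

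- m = 2: 94.6 × 1.59 / 2 = 75.2, so 76 per arm and 152 in total, as stated.
- m = 3: 94.6 × 2.18 / 3 = 68.8, so 69 per arm and 138 in total, as stated. (Rounding 94.6 up to 95 first gives 140.)

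**2. Error of a plainly unadjusted test.** True two-sided error = 2·(1 − Φ(1.96 / √(1 + (m − 1)·ICC))). The stigma ICC is an assumption, so a range is shown.

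| True ICC | m = 2: design effect, error | m = 3: design effect, error |
|---|---|---|
| 0.05 | 1.05, 5.6% | 1.10, 6.2% |
| 0.10 | 1.10, 6.2% | 1.20, 7.4% |
| 0.20 | 1.20, 7.4% | 1.40, 9.8% |

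At ICC 0.20 the unadjusted standard error is 8.7% (m = 2) or 15.5% (m = 3) too small.

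**3. Error of the trigger applied as a rule.** Simulation with no arm effect, normal change scores, equal household sizes, 1:1 allocation and 40,000 replicates per setting (Monte Carlo standard error about 0.1 percentage point). The ICC is estimated within arm by ANOVA. If it exceeds 0.2, household means are compared by t-test; otherwise individuals are compared by t-test.

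| True ICC | 152 × 2: error | Adjustment skipped | 138 × 3: error | Adjustment skipped |
|---|---|---|---|---|
| 0 | 5.0% | | 4.8% | |
| 0.05 | 5.4% | | 6.3% | |
| 0.10 | 5.9% | 89% | 7.2% | 97% |
| 0.15 | 6.1% | 74% | 7.9% | 82% |
| 0.20 | 6.0% | 50% | 7.2% | 51% |
| 0.25 | 5.6% | | 5.7% | |
| 0.30 | 5.3% | 10% | 5.1% | 4% |
| 0.40 | 4.9% | 0.3% | 4.8% | 0.03% |

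Always adjusting gives 4.8–5.3% throughout. Independent repeats put the highest cell (138 × 3, ICC 0.15) between 7.4% and 7.9%; a repeat with 200,000 replicates gives 7.75%.

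**4. Unequal household sizes.** With an assumed coefficient of variation of 0.5 and ICC 0.20, the design effect 1 + ((1 + CV²)·m − 1)·ICC is 1.30 (m = 2) or 1.55 (m = 3). The unadjusted error is then 8.6% or 11.5%.

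**5. Uptake.** Beta-binomial simulation at ICC 0.59, 20,000 replicates: the estimated ICC falls to 0.2 or below in at most 0.4% of trials (152 × 2, 85% v 98%). The trigger would almost never bite on uptake.

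**The case against.** The strongest reply is that no unadjusted test is written anywhere for Aim 2. The clause says when adjustment is required, not that it is dropped otherwise. Every named method is cluster-adjusted or multilevel, so the clause can be read as redundant. This is fair as to the wording: the unadjusted branch is implied, not stated. But if the clause is redundant, deleting it loses nothing. If it is not, it overrides valid methods. The plan does not say which.

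Second, the simulation compares arms with an independent t-test, whereas the plan names dependent t-tests together with multilevel models, and item 13 does not say whether the stigma ICC refers to scores or to change. This also stands: the percentages describe one reasonable reading, not an error rate to which the plan commits itself. The direction does not depend on that choice, because the variance of a mean change within an arm carries the same factor 1 + (m − 1)·ICC. The multilevel model would protect the result if it were the deciding analysis, but the plan does not say that it is.

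Third, the excess is about one percentage point at the target of 152 households of 2, it needs a modest stigma ICC, and this is a pilot. All true, and it limits the weight of the point. It does not justify keeping a rule that can only leave the primary test's error unchanged or raise it.

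**Conclusion.** The concern holds. The trigger is inconsistent with household randomisation and with the unconditional adjusted methods in items 4 and 13, and it could permit an unadjusted test of change in stigma.

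Applied as a rule, it raises the two-sided error from 5% to about 6% (152 households of 2) or 7–8% (138 households of 3) for a true stigma ICC of 0.10–0.20. There is essentially no excess at ICC 0 or at 0.30 and above. These figures assume a between-arm comparison of normally distributed change scores, equal household sizes, and an ICC range that the documents do not supply. Uptake at the planned ICC of 0.59 is practically unaffected. The inflation is moderate, but it falls on the primary outcome and the correction is trivial, so it should be made before the data are analysed.

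**What to change.** In Section I, item 13, delete the 0.2 threshold. State instead that every between-arm analysis of stigma and of uptake accounts for household clustering whatever the estimated ICC, by the adjusted tests and multilevel models already named, and that household ICCs are reported for description only.

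The cost is one clause. The sample size stands, because it already includes the design effect. Where the true ICC is near zero, adjustment costs almost nothing: with 152 households of 2, a household-mean t-test has 150 degrees of freedom against 302 for individuals, so the critical value is 1.976 instead of 1.968.
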